7. STUDY TREATMENTS

ASTX029 (the IMP) will be the only study treatment administered.

7.1. Investigational Medicinal Product (ASTX029)

7.1.1. Drug Substance, Drug Product, and Packaging

ASTX029 is a synthetic small molecule and a new chemical entity.

The molecular formula of the ASTX029 drug substance is

Powder-in-Bottle Dosage Form

One form of the drug product was supplied as a PiB containing 1.0 g or 5.3 g ASTX029 free-base equivalents for reconstitution with a vehicle for reconstitution (VFR), which had been formulated for this compound and was suitable for oral or gastrostomy tube (g-tube) administration.

ASTX029 PiB was supplied in amber glass bottles with screw caps. The bottles were labeled as IMP, in accordance with applicable regulations. There are no inactive ingredients formulated with ASTX029 PiB. The VFR was also supplied in amber glass bottles with screw caps. Each bottle of VFR contained a fill volume of 110 mL. The inactive ingredients in the VFR are: propylene glycol, ethanol, and TPGS (80:10:10%w/w).

Note: The PiB dosage form was phased out after sufficient PK and safety data were collected and with approval from the DSRC. See Section 7.1.6 for further information on the transition to tablets.

Tablet Dosage Form

Amendment 1.0 introduced a tablet dosage form of ASTX029. (Note: tablets cannot be administered by g-tube.) The tablets are provided in sealed bottles with child-resistant closures. Each bottle contains 21 tablets. Bottles are labeled with the tablet strength and are further distinguished by differently colored labels. Please refer to the current ASTX029 IB for further information. The bottles are labeled as IMP, in accordance with applicable regulations. In addition to the tablets, each bottle contains a small white plastic canister built into the cap that contains a desiccant.

The film-coated tablets include the following excipients:

These excipients are of compendial grade and are generally

recognized as safe (GRAS).

7.1.2. Storage

Store ASTX029 tablets per instructions in the pharmacy manual. In the study center, storage should be in a secure, locked facility accessible only to authorized study personnel. ASTX029 tablets will be evaluated under stability protocols designed according to ICH guidelines for shelf-life assignment and, if warranted, shelf life may be extended.

7.1.3. ASTX029 Reconstitution

Tablets are provided in bottles containing 21 tablets each. A sufficient quantity of tablets will be dispensed to the subject to permit oral self-administration at the required dose level for the required number of days.

Records of the receipt and dispensing of drug will be kept at the study centers and reconciled at the end of the study to provide a complete accounting of all used and unused IMP.

7.1.4. ASTX029 Regimens and Dose Levels

In this open-label study, all subjects will receive ASTX029 orally according to the assigned treatment regimen and dose. At any point in the study, the dose of ASTX029 may be reduced, withheld, or discontinued for individual subjects in the event of unacceptable treatment-related toxicity, as described in Section 7.5. No active comparator or placebo is planned for this study.

In Phase 1 Part A, subjects will receive 1 of up to potentially 2 ASTX029 dosing regimens. Subjects in Regimen 1 will receive ASTX029 orally once a day on Days 1 through 21 of each 21-day cycle (Regimen 1; continuous dosing), and, if Regimen 2 is opened to enrollment, subjects in Regimen 2 will receive ASTX029 orally once a day on Days 1 through 14 of each 21-day cycle (Regimen 2; intermittent dosing, 2 weeks on/1 week off).

Initially, subjects will be allocated to Regimen 1 (continuous dosing). Subjects in the first cohort of Regimen 1 will receive a flat starting dose of 10 mg QD (Section 2.2). Dose levels for subsequent cohorts will be determined by the DSRC. Planned initial escalation will be 100% (doubling the dose) until 160 mg. Smaller increments of dose escalation will be used above 160 mg. Dose doubling will also be discontinued if any 1 of the following occurs within a cohort:

- 1 subject experiences a DLT (Section 7.4).
- Any study-drug-related clinically significant ≥Grade 2 AE not adequately managed or resolved to baseline or Grade 1 by supportive treatment that, per the DSRC, indicates further dose doubling would be potentially unsafe for future subjects.
- Any study-drug-related AE or confluence of AEs that, per the DSRC, indicates further dose doubling would be potentially unsafe for future subjects.

After this point, dose escalation will proceed in smaller increments (eg, by a 50% increase initially and an ~25% increase at the higher dose levels over the previous level), after review of all available safety, PK, and biomarker data from Cycle 1 in at least 3 subjects and approval by the DSRC. The DSRC will determine the need to expand to 6 subjects per cohort if 1 subject in the first 3 subjects or if multiple subjects have Grade 2 events that require additional subjects in order to collect additional safety data and better inform dose-escalation decisions. If more than 1 subject has DLTs in any cohort of 3 or 6 subjects, no further escalation should occur of that regimen and exploration of lower dose regimens may be recommended by the DSRC to refine the MTD and the RDE.

[figure not shown]
An example of a possible dose-escalation plan is shown in Table 3, and a possible dose escalation flowchart is shown in Figure 3.

Cohort	Dose Level (mg/day)	Number of Evaluable Subjects Planned	Comments
1	10 mg	3 or 6	Starting dose based on toxicology data (Section 2.2)
2	20 mg	3 or 6	Increase Starting dose by 100%
3	40 mg	3 or 6	Increase Cohort 2 dose by 100%
4	80 mg	3 or 6	Increase Cohort 3 dose by 100%
5	160 mg	3 or 6	Increase Cohort 4 dose by 100%
6	240 mg	3 or 6	Increase Cohort 5 dose by 50%
7	360 mg	3 or 6	Increase Cohort 6 dose by 50%
8	450 mg	3 or 6	Increase Cohort 7 dose by 25%

Table 3: Example of Possible ASTX029 Dose Levels in Part A

Note: The dose levels and escalation shown in this table are for purposes of example only. The Data and Safety Review Committee will decide on actual dose levels and may recommend escalation increments based on emerging safety and pharmacokinetic data or operational concerns. Planned initial escalation will be 100% (doubling the dose) until 160 mg. Smaller increments of dose escalation will be used above 160 mg.

AE=adverse event; DLT=dose-limiting toxicity; DSRC=Data and Safety Review Committee; MTD=maximum tolerated dose; RDE=recommended dose for expansion; TBD=to be determined.

See Section 7.3 for dose-escalation guidelines.

Also, after this point, the sponsor, with approval of the DSRC, will determine if Regimen 2 is to be opened for enrollment. Randomization to either Regimen 1 or Regimen 2 will begin if both regimens are open for enrollment. Should Regimen 2 be evaluated, based on safety and PK data from Regimen 1 and depending on the nature, timing, and severity of observed AEs, the dose for the first cohort of subjects enrolled to Regimen 2 may be escalated to the next level pending approval by the DSRC. If the MTD is reached in 1 regimen before the other regimen, all subsequent subjects will be enrolled, without randomization, to the remaining regimen until the MTD is determined for each regimen evaluated.

After reaching MTD or RDE for Regimens 1 and 2, the DSRC will also advise if it is appropriate to test an alternative intermittent regimen (Optional Regimen 3, eg, 7 days on/7 days off) and will recommend the dose and dosing regimen to be used. The total dose per cycle for the new regimen will not exceed the total safe dose per cycle already established in the first 2 regimens.

The starting dose in each regimen evaluated will be escalated stepwise in successive cohorts of at least 3 evaluable subjects each with additional allowed expansion to 6 subjects (3+3 study design) until the MTD is determined for each regimen.

Dose-escalation/de-escalation decisions will be based on the occurrence of DLTs (defined in Section 7.4) during the first 21-day cycle of each dose level, and the recommendations of the DSRC following review of all available safety, PK, and biomarker data from the completed first cycle of at least 3 subjects in each cohort (as described in Section 7.3). The DSRC will also advise whether or not it is appropriate to proceed to Part B (Dose Expansion).

Part B (Dose Expansion) will commence upon identification of the RDE for at least 1 regimen. The DSRC RDE decision will be based on all available safety, PK, biomarkers, and preliminary activity data from all cycles (including the potential for late or cumulative toxicity).

At any point, the dose level may be reduced for individual subjects in the event of unacceptable treatment-related toxicity (Section 7.5). Planned dose levels, the number of cohorts, and the number of subjects per cohort, may be modified as needed, in response to emerging PK and safety data, and recommendations from the DSRC.

7.1.5. ASTX029 Administration

Subjects will receive instructions for the storage and self-administration of the IMP by oral administration at home (also see Section 9.4.11). However, on visit days, subjects will be asked to wait until they arrive at the study center and are under the supervision of the study staff before they ingest the study drug to ensure accurate recording and timing of blood draws relative to IMP ingestion. When subjects self-administer IMP at home, they are expected to record the date and time of ingestion in their dosing diary, along with any pertinent notes (eg, vomiting after ingestion of the dose).

If a patient forgets to take or misses a dose, they may take the dose up to 4 hours late. After that time, the patient should skip the dose for that day and wait until the next day to resume the normal dosing schedule. The VFR of ASTX029 contains ethanol and propylene glycol (Section 7.1.1). The maximum amount of the alcohol intake from the VFR is estimated to be 3.7 g. (Refer to the pharmacy manual for further information.)

ASTX029 should be ingested at approximately the same time of day on each dosing day, and the actual dosing time should be recorded as above.

Study treatment compliance will be assessed periodically throughout the treatment period. Subjects will be required to return all study treatment syringes (used, unused, and partially used) and all unused tablets to the study center, and to share their dosing diaries with study staff.

ASXT029 was originally introduced into the clinic in the PiB form (Section 7.1.1) and administered under fed conditions (Section 7.1.5). Protocol Amendment 1.0 introduced the tablet dosage form (Section 7.1.6) when it became available. Protocol Amendment 2.0 introduced the evaluation of administration under fasted conditions during Phase 1 Part A dose escalation (Section 7.1.7).

Drug Administration Under Fed Conditions

Based on available preliminary data and the properties of ASTX029, it was expected that doses would be better tolerated and absorbed when consumed with food. Hence, although food-effect studies had not yet been conducted with ASTX029, subjects enrolled in the early stages of dose escalation were requested to ingest the IMP with food, ie, within 30 minutes after a breakfast meal. Subjects receiving ASTX029 under fed conditions are requested to have a balanced breakfast meal. Examples of breakfast meals are:

- Egg(s), toast (or potatoes), and juice (orange, apple, cranberry, or tomato) or coffee/tea.
- Bacon (2 strips), toast (or potatoes), and juice (as above) or coffee/tea.
- Sausage, toast (or potatoes), and juice (as above) or coffee/tea.
- Breakfast sandwich with eggs/sausage/bacon; juice (as above) or coffee/tea.

Other varieties/substitutions can be made as long as the meal provides a similar amount of calories from protein, carbohydrate, and fat and has comparable meal volume and viscosity.

Note: grapefruit juice is not allowed during treatment with ASTX029.

Drug Administration Under Fasted Conditions

Amendment 2.0 introduced the evaluation of fasted administration during Phase 1 Part A. Subjects receiving ASTX029 under fasted conditions will be requested to ingest the study treatment after fasting for at least 2 hours, typically in the morning before breakfast, and to also fast for 2 hours after ingestion of study drug. During the 4-hour fasting period, clear liquids (such as tea, coffee, and water) are allowed; milk, juice, and soup are not allowed. **Note: grapefruit juice is not allowed during treatment with ASTX029.** Please see Section 7.1.7 for further details of transition to fasted administration during Phase 1 Part A.

7.1.6. Transition From Powder-in-Bottle Dosage Form to Tablet Dosage Form

With Protocol Amendment 1.0, the tablet form was introduced and replaced the PiB formulation. Transition to the tablet dosage form occurred by dosing a tablet-bridging cohort of 6 subjects at 80 mg/day, a dose that did not exceed the highest PiB dose level in Regimen 1 at which no DLTs were observed as determined by the DSRC assessment of all safety and PK data at the time of initiation of the tablet-bridging cohort. Because the tablet dose was shown to be safe and no

other issues were identified, dose escalation using the tablet dosage form proceeded in subsequent cohorts as described in Section 4.1.1, Table 3, with approval of the DSRC. If the tablet dosing form had not been safely tolerated, dose de-escalation could have occurred as described in Section 7.3 and Section 7.5. Based on review of safety and PK data, the DSRC could have allowed transition of ongoing subjects still receiving PiB to tablets. At the time of Amendment 4.0, all subjects who received ASTX029 PiB had discontinued study drug.

7.1.7. Transition From Fed to Fasted Administration

At the time of Amendment 2.0, dose escalation (Phase 1 Part A) was ongoing. In Phase 1 Part A, ASXT029-01 dose was escalated in sequential cohorts from 10 mg/day to 200 mg/day QD using the PiB form in fed subjects. One DLT (Grade 3 nonserious maculo-papular rash) was reported in the 200-mg/day PiB cohort. Six subjects were enrolled in the tablet-bridging cohort at 80 mg/day QD under fed conditions with no DLTs being reported, and enrollment was ongoing in the 120-mg/day QD tablet cohort.

Preliminary PK data at the time of Amendment 2.0, showed relatively high variability for systemic exposures after ASTX029 was dosed with food. The geometric mean (CV%) plasma AUC_{0-inf} values on C1D1 were 2377(170) ng•h/mL for the 80-mg tablet-bridging cohort (n=4), compared with 4053(83) ng•h/mL for the 120 mg PiB (n=5) cohort and 8304(53) ng•h/mL for the 200 mg PiB cohort (n=9).

With Protocol Amendment 2.0, administration under fasted conditions was introduced. Fasted administration may result in higher exposure of ASTX029 at lower doses (Section 1.3.2.1) and potentially reduce intersubject variability compared with administration with food.

Transition to fasted-state dosing occurred during Phase 1 Part A by dosing a bridging cohort of 3 subjects at a dose of 40 mg/day tablets QD. Starting with Amendment 3.0, dose escalation under fed conditions was discontinued, and dose escalation under fasted conditions is ongoing. Please refer to the current ASTX029 IB for preliminary PK and safety data.

7.2. Active Comparator or Placebo

No active comparator or placebo is planned for this study.

7.3. Dose-Escalation Guidelines and Recommended Phase 2 Dose Decision

Dose-escalation/de-escalation decisions will be based on the occurrence of DLTs (defined in Section 7.4) during the first cycle of each dose level, and the recommendations of the DSRC following review of all available safety, PK, and biomarker data from the completed first cycle of at least 3 subjects in each cohort (Section 4.4). The DLT-based dose-escalation guidelines are summarized below.

Intrasubject escalations will not be allowed; however, once an MTD or RDE dose level is determined, active subjects may be allowed to receive their subsequent cycles at that dose level at the investigator's discretion with prior Sponsor approval.

First 3 Subjects in a Cohort

- If no subjects among the first 3 (<33%) experience a DLT, the dose may be escalated to the next higher level for the next cohort of 3 subjects.
- If 1 subject among the first 3 (33%) experiences a DLT, the cohort size will be increased to 6 subjects.
- If 2 subjects among the first 3 (>33%) experience a DLT, the previous dose level (ie, 1 step below) would be declared the MTD.

Expanded Cohort of 6 Subjects

- If no more than 1 subject in the cohort of 6 (ie, a total of 1 out of 6, <33%) experience a DLT, the dose may be cautiously escalated (~25% increase) to the next higher level for the next cohort of 3 subjects.
- If 2 subjects in the cohort of 6 (33%) experience a DLT, that dose level or the previous dose level (ie, 1 step below) would be declared the MTD for the regimen. The DSRC may recommend exploration of intermediate doses before an MTD is declared.
- If more than 2 subjects in the cohort of 6 (>33%) experience a DLT, the previous dose level (ie, 1 step below) would be declared the MTD for the regimen. The DSRC may recommend exploration of intermediate doses before an MTD is declared.

Recommended Dose for Expansion

The RDE is defined as either the MTD or a dose below the MTD that the DSRC agrees shows adequate safety, PK and/or preliminary biological activity, or clinical activity for a regimen. One or more dose levels (and regimens) may be studied in Phase 1 Part B to supplement available safety, PK, and/or clinical activity data and to evaluate target engagement in fresh tumor tissue biopsies. The RDE decision by the DSRC will be based on all available safety, PK, biomarkers, and preliminary activity data from all cycles (including potential for late or cumulative toxicity) from Phase 1 Part A.

Recommended Phase 2 Dose

The RP2D is defined as the dose that the DSRC agree shows adequate safety, PK, pharmacodynamic, and/or biological or clinical activity to warrant further investigation in the Phase 2 part of this study. The RP2D decision by the DSRC will be based on all available PK, biomarker, safety, and preliminary clinical activity data from all cycles, including potential for late or cumulative toxicity from Phase 1 Parts A and B. The RP2D could be the same or lower than the RDE.

Based on the data presented in Section 1.3.3, the DSRC determined the RP2D to be 200 mg administered orally daily, continuously, in 21-day cycles under fasting conditions.

7.4. Definition of Dose-Limiting Toxicities

Dose-limiting toxicities are AEs (graded by National Cancer Institute (NCI) Common Terminology Criteria for Adverse Events (CTCAE) v4.03 criteria [Appendix 2]) that occur during the first cycle of treatment and represent any 1 of the following, unless there is a clear alternative cause of the event (eg, disease progression, disease-related):

- Grade 4 thrombocytopenia of any duration.
- Erade 3 hematologic toxicity with complications (eg, Grade 3 thrombocytopenia with bleeding or transfusion requirement).
- Febrile neutropenia of any duration or Grade 4 neutropenia of 5 days or more duration.
- Liver-associated abnormalities defined as:
 - – ≥Grade 3 bilirubin, ALT, or AST elevation, except ALT or AST elevation
 >5×ULN and <8×ULN for <7 days.

 - ALT or AST >3×ULN AND either total bilirubin >2×ULN OR international normalized ratio (INR) >1.5.
 - ALT or AST >3×ULN with clinical indications of liver toxicity (signs, symptoms, or other diagnostic findings).
- \geq Grade 2 eye disorders (ocular toxicities) that do not improve to \leq Grade 1 within 7 days despite treatment discontinuation or documented RVO.
- Symptomatic Grade 2 cutaneous toxicities (including skin rash) that do not improve to ≤Grade 1 within 7 days despite supportive treatment and treatment discontinuation.
- Any other ≥Grade 3 nonhematologic AE except Grade 3 nausea, vomiting, or diarrhea that resolves to ≤Grade 1 by symptomatic treatment within 24 hours.
- Any event that, in the opinion of the DSRC, would suggest that further dose escalation would put subjects at unacceptable risk.

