ASXT029 was originally introduced into the clinic in the PiB form (Section 7.1.1) and administered under fed conditions (Section 7.1.5). Protocol Amendment 1.0 introduced the tablet dosage form (Section 7.1.6) when it became available. Protocol Amendment 2.0 introduced the evaluation of administration under fasted conditions during Phase 1 Part A dose escalation (Section 7.1.7).

At the time of writing Protocol Amendment 4.0, the COVID-19 pandemic is altering the way clinical studies are being conducted such that alternative measures are being implemented to ensure the safety of subjects and maintain the integrity of clinical trial data. Appendix 9 details information regarding potential modifications to the conduct of the study during the pandemic.

4.1.1. Phase 1

The Phase 1 portion of the study will consist of Parts A and B as follows:

Part A (Dose Escalation): The dose-escalation stage will identify the MTD of up to 2 dosing regimens of ASTX029 and the recommended dose for expansion (RDE), defined as either the MTD or a dose below the MTD that the DSRC agrees shows adequate safety, PK, and/or preliminary biological or clinical activity.

Subjects will receive 1 of up to potentially 2 ASTX029 dosing regimens. Subjects in Regimen 1 will receive ASTX029 orally once a day on Days 1 through 21 of each 21-day cycle (Regimen 1; continuous dosing), and, if Regimen 2 is opened to enrollment, subjects in Regimen 2 will receive ASTX029 orally once a day on Days 1 through 14 of each 21-day cycle (Regimen 2; intermittent dosing, 2 weeks on/1 week off).

Initially, subjects will be allocated to Regimen 1 (continuous dosing). Subjects in the first cohort of Regimen 1 will receive a flat starting dose of 10 mg QD. Dose levels for subsequent cohorts will be determined by the DSRC. Planned initial escalation will be 100% (doubling the dose) until 160 mg. Smaller increments of dose escalation will be used above 160 mg. Dose doubling will also be discontinued if any 1 of the following occurs within a cohort:

- 1 subject experiences a DLT (Section 7.4).
- Any study-drug-related clinically significant ≥Grade 2 AE not adequately managed or resolved to baseline or Grade 1 by supportive treatment that, per the DSRC, indicates further dose doubling would be potentially unsafe for future subjects.
- Any study-drug-related AE or confluence of AEs that, per the DSRC, indicates further dose doubling would be potentially unsafe for future subjects.

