7.5. Guidelines for Adjusting, Withholding, or Discontinuing Study Treatment

ASTX029 dosing should be withheld in the case of a DLT in Cycle 1 or toxicity in subsequent cycles that would have qualified as a DLT if it had occurred in Cycle 1. Dosing may resume, at the investigator's discretion, if and when study-treatment-related toxicity has:

- Completely resolved or
- Returned to baseline or partially recovered to ≤Grade 2 (anemia, fatigue, malaise, and alopecia) or returned to baseline or partially recovered to ≤Grade 1 (all other toxicities).

If and when a decision is made to resume dosing, the individual's dose should be adjusted to the previously assessed lower dose level that was considered safe by the DSRC. A maximum of 2 dose reductions are permitted for any single subject. In the event of further unacceptable toxicity, the investigator should consider discontinuation of study treatment for that subject.

If toxicity has not resolved as described above within 21 days, the investigator should permanently discontinue study treatment unless the subject is receiving compelling benefit, the

benefit of the study treatment exceeds the risks, and no alternative therapy is available. Approval by the Sponsor's medical monitor is required to restart study treatment after an interruption \geq 21 days, and study treatment must be administered at a dose approved by the Sponsor's medical monitor when toxicity has resolved as described above.

Suggested guidelines and criteria for adjusting, withholding, or discontinuing study treatment as a result of skin toxicities, ocular toxicities, diarrhea, liver toxicities, and LVEF decrease are provided in Appendix 4, Appendix 5, Appendix 6, Appendix 7, and Appendix 8, respectively. The institutional standards for the management of these toxicities can differ from the suggested guidelines. In this case, best clinical judgment should be applied.

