APPENDIX 4. MANAGEMENT OF SKIN TOXICITIES

Cutaneous adverse events have been observed in subjects receiving MEK inhibitors (ie, trametinib [Mekinist USPI] and cobimetinib [Cotellic USPI]) and ERK inhibitors (ulixertinib and GDC-0994) (de la Cruz-Merino et al 2017; Sullivan et al 2018; Li et al presentation 2017, Varga et al 2020; Infante et al abstract 2015; Infante et al presentation 2015; Macdonald et al 2015; Reyes-Habito et al 2014; Anforth et al 2013; Mandalà et al 2013; Manousaridis et al 2013).

Suggested guidelines regarding management and criteria for adjusting, withholding, and discontinuing study treatment for skin toxicities considered to be related to study treatment are provided in Table 15. The institutional standards for the management of skin-related AEs can differ from these guidelines. In this case, best clinical judgment should be applied.

CTCAE		
Grade	Management	Action and Dose Modification
Grade 1	 Initiate symptomatic measures. Use moderate strength topical steroid.^a Consider topical antibiotics or combined topical steroids/antibiotics if acneiform papulopustular rash. Consider oral antibiotics. Consider oral antihistamines if maculopapular rash. Reassess after 1 week. 	 Continue study treatment and monitor for change in severity. If no recovery to ≤Grade 1 within 2 weeks despite best supportive care, reduce study treatment by 1 dose level.^b
Grade 2	 Initiate symptomatic measures. Use moderate strength topical steroid.^a Obtain bacterial/viral/fungal cultures if infection is suspected. Initiate topical antibiotics and, if rash is persistently ≥Grade 2 after 1 week, initiate oral antibiotics for 6 weeks (doxycycline 100 mg BID or minocycline 100 mg BID) if acneiform papulopustular rash. Initiation of oral antibiotics at first sign of Grade 2 acneiform papulopustular rash is also appropriate. Initiate oral antihistamines or oral steroid^c if maculopapular rash. Consider dermatology referral for evaluation and biopsy. Reassess after 1 week. 	 Reduce study treatment by 1 dose level. After reduction, if recovery to ≤Grade 1, increase dose to previous dose level. After reduction, if no recovery to ≤Grade 1 within 1 week, interrupt study treatment until recovery to ≤Grade 1 and restart with study treatment reduced by 1 dose level.^d

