APPENDIX 7. LIVER STATUS MONITORING AND MANAGEMENT OF POTENTIAL LIVER INJURY

Liver enzyme elevation has been observed in patients receiving ERK inhibitors (Sullivan et al 2018; Li et al presentation 2017; Varga et al 2020; Infante et al abstract 2015; Infante et al presentation 2015). Clinical symptoms and laboratory test values that are potential signals of liver injury must be regularly reviewed by investigators and by the Sponsor's medical monitor for the study.

Discontinuation of study treatment should occur if a subject shows potential signals of liver injury, indicated by the occurrence of any of the following liver function test values. (Note: liver toxicity or injury may be confirmed with a liver biopsy, if clinically indicated.)

- ALT or AST $\geq 8 \times ULN$.
- ALT or AST >5×ULN but <8×ULN for \geq 7 days.
- ALT or AST >3×ULN and either total bilirubin >2×ULN or INR >1.5, if INR measured.
- ALT or AST >3×ULN with clinical indications of liver toxicity (signs, symptoms, or other diagnostic findings).
- ALT or AST >5×ULN but <8×ULN and subject cannot be closely monitored as described below.

Subjects with potential signals of liver injury must be closely monitored as described below:

- Report the event to the Sponsor's medical monitor.
- Repeat liver enzymes, total bilirubin, and INR at least twice weekly until liver function test elevations resolve or stabilize or the values return to baseline. (The frequency of retesting can decrease to once a week or less if abnormalities stabilize and the subject is asymptomatic.)
- Obtain a detailed history of symptoms, including any prior and concurrent diseases.
- Obtain a history of concomitant drug use (including nonprescription medications and herbal and dietary supplement preparations), alcohol and recreational drug use, and any special diets consumed.
- Rule out acute viral hepatitis (types A, B, C, D, and E), autoimmune or alcoholic hepatitis, nonalcoholic steatohepatitis, hypoxic/ischemic hepatopathy, and biliary tract disease.
- Obtain a history of exposure to environmental chemical agents.
- Review additional tests to evaluate liver status, as appropriate. If alkaline phosphatase (ALP) is elevated, perform an analysis of ALP isoenzymes to determine if the origin of the ALP elevation is bone or liver.
- Consider scheduling the subject for gastroenterology or hepatology consultation.
- Collect ad hoc PK samples.

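### The same liver signal may be restarted under Protocol 7.5 but is an unqualified stop in Appendix 7, and the Grade 2 rash DLT test in 7.4 needs a stop that Table 15 does not make first

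*Protocol*

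**What the plan says.** Protocol 7.4 defines DLTs as adverse events "that occur during the first cycle of treatment and represent any 1 of the following". The list includes several liver patterns, among them ALT or AST above 3×ULN together with bilirubin above 2×ULN or INR above 1.5. For skin it includes "Symptomatic Grade 2 cutaneous toxicities (including skin rash) that do not improve to ≤Grade 1 within 7 days despite supportive treatment and treatment discontinuation".

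Section 7.5 states that "ASTX029 dosing should be withheld in the case of a DLT in Cycle 1 or toxicity in subsequent cycles that would have qualified" under the DLT criteria. Dosing may then resume at the investigator's discretion once the toxicity has recovered as specified, at a lower dose level that the DSRC considered safe. No organ system is exempted. The section refers to Appendices 4 to 8 for suggested guidance and allows institutional standards to differ.

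Appendix 7 says "Discontinuation of study treatment should occur if a subject shows potential signals of liver injury" and lists five patterns, which its last paragraph calls stopping criteria. It does not say whether the stop is temporary, and it gives no restart condition.

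For Grade 2 skin events, Table 15 in Appendix 4 begins with a reduction of one dose level and continues: "After reduction, if no recovery to ≤Grade 1 within 1 week, interrupt study treatment until recovery to ≤Grade 1". The synopsis places individual dose reductions after Cycle 1, whereas 7.1.4 allows them at any point.

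Section 7.3 records that the Phase 2 dose has been chosen. SAP 7.6.3 summarizes Phase 1 DLTs from the indicator on the AE eCRF.

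**The concern.** An investigator who sees a liver signal has two places to look. Section 7.5 leads to a hold and a possible restart at a lower dose. Appendix 7 can be read as the end of treatment. The choice decides whether a subject is re-exposed after a possible liver injury, and it also affects exposure and discontinuation summaries. The issue applies to every subject still on treatment, including Phase 2.

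For rash, the DLT criterion is conditional on treatment having been stopped, yet the protocol's own skin guidance does not stop it at the first step. DLT incidence is a Phase 1 primary endpoint. If the criterion can be completed only on some management paths, whether and when a given rash is flagged depends on which text the site followed. The toxicology section itself notes that delayed rash has been seen clinically with ERK and MEK inhibitors, so onset late in Cycle 1 is foreseeable.

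**Working it through.** The plan states no figure on this point, so there is none to reproduce. The check sets the sections side by side and then counts days.

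**Liver.** The exception in 7.4 implies that Grade 3 ALT or AST begins above 5×ULN. On that reading:

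| Pattern | DLT in 7.4 | Stop in Appendix 7 |
|---|---|---|
| ALT/AST ≥8×ULN | yes | yes |
| ALT/AST >5 to <8×ULN for ≥7 days | yes | yes |
| ALT/AST >3×ULN with bilirubin >2×ULN or INR >1.5 | yes | yes (INR if measured) |
| ALT/AST >3×ULN with clinical indications | yes | yes |
| ALT/AST >5 to <8×ULN for <7 days, close monitoring not possible | not listed | yes |
| Bilirubin Grade ≥3 alone | yes | no |

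Four patterns are on both lists. For these, 7.5 gives hold, recover, resume lower; Appendix 7 gives discontinuation and nothing further.

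The word *discontinuation* does not settle it:

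- Towards temporary: 7.4 uses the same word in tests read after 7 days, following which 7.5 allows resumption. Section 7.5 and Appendices 4, 5, 6 and 8 add *permanently* when they mean it.
- Towards permanent: Appendix 7 speaks of stopping criteria and contrasts them with milder elevations in which the drug may be continued. The other appendices use *interrupt* or *withhold* for a pause and state when dosing can restart.

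**Rash, logic.** The 7.4 test needs drug to have been stopped. Table 15 stops it only after a failed week on a reduced dose. Section 7.5 does not supply an earlier stop, because it withholds only once a DLT or its later-cycle equivalent exists, and this DLT presupposes the stop. The comparable eye criterion does not have this gap: Table 16 interrupts treatment at once at Grade 2.

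**Rash, day count.** Inputs:

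- Cycle length is 21 days ("ASTX029 orally once a day on Days 1 through 21 of each 21-day cycle"; SAP 7.9 confirms that only this regimen opened).
- The persistence test takes 7 days (7.4).
- The reduced-dose step takes 1 week (Table 15).

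For onset on day d and lag L, status is known by Day 21 if d + L ≤ 21.

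- 7.4 alone, drug stopped at onset: L = 7, so d ≤ 14. Days 15-21 are pending (7 of 21).
- Table 15 first, 7 days counted from interruption: L = 7 + 7 = 14, so d ≤ 7. Days 8-21 are pending (14 of 21).
- Added by the mismatch: Days 8-14, that is 14 − 7 = 7 of 21.

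If status may be read at Cycle 2 Day 1 (Day 22), the pending days are 16-21 (6) and 9-21 (13), and the difference is still 13 − 6 = 7 days. By visit, a rash found on Day 8 is settled on Day 15 or Day 22; one found on Day 15 is settled on Day 22 or Day 29.

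The 14-day lag assumes that reduction is permitted within Cycle 1, where the synopsis and 7.1.4 disagree, and that the clock starts at interruption, which no section states.

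**The case against.** On the liver, the defence is that 7.5 is general and permissive, refers to Appendix 7 for liver toxicity, and that each signal must be reported to the medical monitor. Divergent handling would therefore be seen. That limits the harm but does not supply a rule: nothing says that Appendix 7 overrides 7.5, and it still lacks a restart condition.

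On the rash, much of the defence stands. Table 15 is suggested guidance and does not bar stopping at onset. The DSRC can declare a DLT on its own judgement, can expand a cohort for multiple Grade 2 events (7.1.4), and bases the expansion and Phase 2 doses on data from all cycles (7.3).

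A reader might infer several stronger things that the documents do not support:

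- *Late rashes have no DLT status.* Section 7.4 requires the event to occur in Cycle 1, not its 7-day outcome to be known by Day 21. Status is pending, and the DSRC could wait for it.
- *Table 15 leaves two thirds of onset days open.* Days 15-21 are open from the 7-day test alone.
- *The DLT reported in 7.1.7 shows the effect.* That rash was Grade 3 and falls under the general Grade 3 nonhematologic criterion, without the Grade 2 persistence test.
- *In later cycles 7.5 withholds for an event that Table 15 treats at a reduced dose.* A new Grade 2 rash does not trigger 7.5, because it has not yet met the DLT-equivalent test.
- *The DLT count is biased down and escalation went too far.* This would need the true DLT rate, the share of DLTs that turn on this criterion, and evidence that pending rashes were scored as non-DLTs. The documents give none of these.

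**Conclusion.** The liver point holds in full. For four patterns on both lists, 7.5 and Appendix 7 leave restart undetermined, and following one or the other can lead to opposite handling of the same subject. It is the main point because it governs current treatment.

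The rash point holds in a narrower form. The 7.4 test rests on a stop that Table 15 delays by a week and 7.5 does not provide, and there is no stated clock start or rule for a rash still pending at the end of Cycle 1. On the stated assumptions the mismatch adds 7 onset days (Days 8-14) to the 7 that are pending anyway. With the Phase 2 dose fixed, the remaining consequences are the consistency of the Phase 1 DLT summary and the later-cycle trigger in 7.5, which inherits the same unclear test. No error in past escalation decisions follows from this.

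**What to change.** Reconcile 7.5 with Appendix 7 so that each liver pattern carries one instruction on stopping and on whether and how treatment may restart. Say which text governs if they differ, and use *withhold* and *permanently discontinue* consistently. Check at the same time the two patterns that appear on only one list.

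Reconcile 7.4, 7.5, Table 15, 7.1.4 and the synopsis for Grade 2 skin events. State whether reduction within Cycle 1 is permitted, when the 7 days begin, and how an event pending at the end of Cycle 1 is counted. For Phase 1 data already collected, SAP 7.6.3 should state the counting convention used for the DLT table.

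Which clinical rule applies is for the sponsor's clinicians. The cost is wording. Section 14.4 allows an administrative letter for obvious inconsistencies; a change in the substance of a stopping or restart rule would need an amendment. No new data collection is required.
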